6.0 Delays / Modifications to Imaging Studies Schedule

In case the patient is not able to complete all the required imaging procedures within 8 weeks, patient will be replaced. However patients who completed all the standard imaging studies (CT scan and bone scan) and at least one newer imaging study (WB/axial MRI, F-18 NaF PET/CT) will be considered for analysis. Patients who decline recommended biopsy will not be excluded from analysis.

7.0 Data and Safety Monitoring

7.1 Definition of Risk Level

This is a Risk Level 2 study, as defined in the “City of Hope Data and Safety Monitoring Plan”, <http://www.coh.org/dsmc/Pages/forms-and-procedures.aspx> because it involves imaging studies and biopsies where the risk of harm is low.

7.2 Monitoring and Personnel Responsible for Monitoring

The PI is responsible for monitoring protocol conduct. The PI will report to the COH DSMC any deviations, adverse events and/or serious adverse events related to study procedures and report unanticipated problems to the DSMC and IRB.

7.3 Definitions

Adverse Event - An adverse event (AE) is any untoward medical experience or change of an existing condition that occurs during or after treatment, whether or not it is considered to be related to the protocol intervention.

Serious Adverse Event (SAE) [21 CFR 312.32] is defined as any expected or unexpected adverse event that results in any of the following outcomes:

- Death
- Life-threatening experience (places the subject at immediate risk of death from the event as it occurred);
- Unplanned hospitalization (equal to or greater than 24 hours) or prolongation of existing hospitalization;
- A persistent or significant disability/incapacity;
- A congenital anomaly/birth defect
- Secondary Malignancy, or
- Any other adverse event that, based upon appropriate medical judgment, may jeopardize the subject's health and may require medical or surgical intervention to prevent one of the outcomes listed above (examples of such events include allergic bronchospasm requiring intensive treatment in the emergency room or at home, blood dyscrasias of convulsions that do not result in inpatient hospitalization, or the development of drug dependency or drug abuse).

Unanticipated problem (UP) – Any incident, experience or outcome that meets all three of the following criteria:

1. Unexpected (in term nature, severity, or frequency) given the following: a) the research procedures described in the protocol-related documents such as the IRB approved research protocol, informed consent document or Investigator Brochure (IB); and b) the characteristics of the subject population being studied; **AND**
2. Related or possibly related to participation in the research (possibly related means there is a reasonable possibility that the incident, experience, or outcomes may have been caused by the drugs, devices or procedures involved in the research); **AND**
3. Suggests that the research places subjects or others at greater risk of harm (including physical, psychological, economic, or social harm) than previously known or recognized.

7.4 Reporting of Unanticipated Problems and Adverse Events

Unanticipated Problems: Unanticipated problems must be reported to the COH DSMC and IRB **within 5 calendar days** according to definitions and guidelines at <http://www.coh.org/hrpp/Pages/hrpp-policies.aspx>. Any unanticipated problem that occurs during the study conduct will be reported to the DSMC and IRB by submitting electronically in iRIS (<http://iris.coh.org>).

Serious Adverse Events - All SAEs occurring during this study, whether observed by the physician, nurse, or reported by the patient, will be reported according to definitions and guidelines at <http://www.coh.org/hrpp/Pages/hrpp-policies.aspx> and Table 1 below. Those SAEs that require expedited reporting will be submitted electronically in iRIS (<http://iris.coh.org/>).

Adverse Events - Adverse events will be monitored by the PMT. Adverse events that do not meet the criteria of serious OR are not unanticipated problems will be reported only in the protocol continuation reports (see Table 1 below).

Table 1: City of Hope Adverse Event and Unanticipated Problem Reporting Timelines for the DSMC and IRB

Required Reporting Timeframe to DSMC		
Attribution	UNEXPECTED	EXPECTED
	Death while on active treatment or within 30 days of last day of treatment	
Possibly, Probably, Definitely	5 calendar days	
Unlikely, Unrelated		
	Death after 30 days of last active treatment/therapy	
Possibly, Probably, Definitely	5 calendar days	No reporting required*
Unlikely, Unrelated	No reporting required*	No reporting required*
	Grades 3 and 4 AND meeting the definition of “serious”	
Possibly, Probably, Definitely	5 calendar days	5 calendar days
Unlikely, Unrelated	5 calendar days	5 calendar days
	Grade 1 and 2 AND resulting in hospitalization[#]	
Possibly, Probably, Definitely	5 calendar days	10 calendar days
Unlikely, Unrelated	10 calendar days	10 calendar days

*Such events are not required to be reported to the DSMC. These events should be included with the SAE/AE summary provided in the IRB Annual Continuation reports.

Hospitalization = Unplanned admission equal to or greater than 24 hours

Required Reporting Timeframe to IRB of Record		
Attribution	UNEXPECTED	EXPECTED
	Death	
Possibly, Probably, Definitely	5 calendar days	Annual
Unlikely, Unrelated	Annual	Annual
	Grades 3 and 4 AND meeting the definition of a UP	
Possibly, Probably, Definitely	5 calendar days	Annual
Unlikely, Unrelated	Annual	Annual
	Grade 1 and 2 AND meeting the definition of a UP	
Possibly, Probably, Definitely	5 calendar days	Annual
Unlikely, Unrelated	Annual	Annual

8.0 Risks

8.1 CT scan

There is a slight risk of developing an allergic reaction to the iodine contrast material. This reaction can be mild (itching, rash) or severe (difficulty breathing or sudden shock). Death resulting from an allergic reaction is rare. Most reactions can be controlled by the use of additional drugs to prevent the allergic type reaction. Participants should inform their doctor if they have allergies of any kind (such as hay fever, iodine allergy, [eczema](#), hives, or food allergies). The contrast material used during a CT scan can also cause water loss or damage to the kidneys that may lead to kidney failure. This is of particular concern if there is underlying poor kidney function, dehydration, or [diabetes](#). Participants will be exposed to a limited and medically acceptable dose of radiation during the procedure. There is always a slight risk from being exposed to any radiation, including low levels of X-rays used for a CT scan. Participants may also experience discomfort related to lying still in an enclosed space for a prolonged period of time.

8.2 Bone scan

There is a slight risk of developing an allergic reaction to the contrast material.. This reaction can be mild (itching, rash) or severe (difficulty breathing or sudden shock). Death resulting from an allergic reaction is rare. Most reactions can be controlled by the use of additional drugs to prevent the allergic type reaction. Participants should inform their doctor if they have allergies of any kind (such as hay fever, iodine allergy, eczema, hives, or food allergies). There is always a slight risk from being exposed to any radiation, including low levels used for a bone scan. Participants may also experience discomfort related to lying still in an enclosed space for a prolonged period of time.

8.3 PET/CT

The tracer used in the PET/CT scan is radioactive but short lived and poses little to no risk. Participants may experience claustrophobia from being inside the PET/CT scan or experience mild discomfort from lying on the PET scanner table. A sedative such as Diazepam or lorazepam may be prescribed if participant is unable to relax, lie still, or for those who experience claustrophobia. There can be side effects from diazepam or lorazepam. The more common side effects are:

- Drowsiness which is temporary and may require additional medication
- Dizziness which is temporary and may require additional medication
- Dry mouth which is temporary and may require additional medication
- Diarrhea which is temporary and may require additional medication
- Upset stomach which is temporary and may require additional medication
- Blurred vision which is temporary and may require additional medication

Participants may experience pain and tenderness, bruising or a skin reaction at the injection site when given the study drug injection that will be administered through an intravenous (IV) catheter. As with any IV placement, there is a risk of infection at the site but the careful and clean procedure used for placing the IV almost completely removes this risk.

8.4 MRI

Risks include possible anxiety and claustrophobia related to being placed in the large body scanner; temporary discomfort related to having to lie still during the procedure; and possible pain, infection and bleeding related to venipuncture if contrast dye is used. Because MRI works through a powerful magnetic field, it cannot be done if participants have a pacemaker, intracranial aneurysm clips or other metal implants (for example, types of implants used in eye surgery or orthopedic [bone] surgery), artificial limbs and other medical devices that contain iron. Also, there is a risk that metal objects coming near the magnet may become dangerous as they are pulled toward the magnet. The magnetic field will stop a watch that is within several yards of the magnet. Severe injury or death can occur when subjects with implanted neurological stimulators undergo MRI scans. Participants should discuss any metal devices in their body with the study staff. In addition, when having an MRI scan, iron pigments in tattooed eyeliner or in eye makeup can potentially cause temporary skin irritation and/or swelling around the eye. For subjects that need an MRI scan and have reduced kidney function there is a chance of developing "nephrogenic systemic fibrosis," a condition characterized by thickening and itchiness of the skin, stiffening of the joints and possible reduction in the ability to move around. This condition is associated with the MRI contrast agent gadolinium and occurs mostly in subjects with severe kidney disease. The risk to subjects with mild kidney problems is anticipated to be small. Participants will be questioned and examined, if necessary, to confirm that they may undergo MRI scanning without additional risk. An x-ray may be performed to rule out the presence of a suspected foreign body before the MRI.

8.5 Biopsy

Biopsy will be recommended in selected patients (Table1)

Risks of biopsy will depend on the site of biopsy and patient's underlying medical conditions like potential coagulopathy. Risks include: Pain and discomfort, bleeding at the biopsy site, tenderness at the biopsy site, scarring at the biopsy site, rarely, an infection at the biopsy site.

9.0 Study Calendar

Table 1 Schedule of Events (time scale in weeks)

[figure not shown]
	Week						
	Pre-Study *	1-8	1-8	1-12	16-24	28-36	40-52
Informed consent	X						
Demographics	X						
Medical history	X						
Physical exam	X				X	X	X
Performance Status	X				X	X	X
CBC w/diff, plts	X				X	X	X
Serum chemistry ^a	X				X	X	X
PSA	X				X	X	X
Testosterone	X				X	X	X
Radiologic evaluation (bone scan, CT chest abd / pelvis ^b)		X			X ^f		
Targeted (Xrays) ^c		X			X ^f		
WB/axial MRI, F-18 NaF PET/CT ^d			X		X ^f		
Biopsy of suspected abnormality ^e				X			

* Prestudy tests should be performed within 8 weeks of registration.

- a) Albumin, alkaline phosphatase, total bilirubin, bicarbonate, BUN, calcium, chloride, creatinine, glucose, potassium, total protein, SGOT[AST], SGPT[ALT], sodium.
- b) If bone scan and/or CT scan and/or targeted X-rays were already performed before study registration they can be utilized for the study purposes under late registration provision, provided that patients can be registered and complete WB/axial MRI and F-18 NaF PET/CT within 8 weeks of the oldest standard study.
- c) If recommended by radiologist due to inconclusive findings on bone scan and CT scans.
- d) WB/axial MRI F-18 NaF PET/CT will be performed AFTER bone scan, CT scan and (if needed) targeted X-rays have been completed. All the imaging studies should be completed within 8 weeks of registration (except under late registration provision – see b).
- e) In patients in whom the results of WB/axial MRI and /or F-18 NaF PET/CT are consistent with recurrence or indeterminate.
- f) In patients in whom the results of all the imaging studies and biopsy (if performed) were not conclusive for metastasis. The specifics of which imaging study (or studies) to be performed at week 16- 24 will be determined based on the recommendation of radiologist.

10. Endpoint Evaluation Criteria/Measurement of Effect

All scans will be interpreted by two board-certified radiologists with CT, MRI and nuclear medicine expertise who will be dedicated members of the research team. In cases of differences in interpretation between the two radiologists, the final reading will be determined by consensus conference involving a third radiologist, also a dedicated member of the research team. One of the three possible outcomes will be assigned to the combination of CT scan and BS (and TXR) if obtained: 1) consistent with visible recurrence 2) indeterminate or 3) negative.

Biopsy, when feasible recommended in all patients with MRI or NaF PET/CT consistent with recurrence or indeterminate Record PSA response to Salvage Therapy (if given), perform 4-6 month follow up scans if clinically indicated and follow for 1yr or until progression

Patients who have CT scan and /or bone scan that are consistent with or indeterminate for metastases will be managed in a standard fashion at the discretion of treated physician. It may include additional imaging studies, biopsies and subsequent therapy. Patients with CT scan and bone scan interpreted as negative (estimated $\geq 90\%$) will undergo additional imaging, including WB/axial MRI and F-18 NaF PET/CT. Possible outcomes :1) consistent with recurrence 2) indeterminate 3) negative will be assigned to WB/axial MRI and F-18 NaF PET/CT. In cases of WB/axial MRI interpreted as consistent with visible recurrence or indeterminate a biopsy of the lesion of interest will be recommended if feasible.

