Patients who were classified as having negative bone scan and CT scan (estimated $\geq 90\%$ of patients) will undergo MRI (axial MRI and WB MRI) and F-18 NaF PET/CT. The outcome of these studies will be reported as 1) consistent with visible recurrence, 2) indeterminate 3) negative. In cases of findings consistent with visible recurrence or indeterminate a biopsy of the lesion of interest will be recommended if feasible. Any enrolled patient without a positive biopsy will be followed and their treatment (at discretion of treating physician), PSA values and outcome will be recorded to evaluate the scan result specificity and sensitivity in relation to additional information provided with follow-up (e.g. if patients undergo Salvage Radiation Therapy, PSA response will be recorded which will have significant implication in the interpretation of radiologic findings (see 10). Subsequently all patients without biopsy proven metastasis will undergo follow up imaging studies (the type of imaging to be recommended by radiologist)) within 4-6 months to reassess any abnormalities in the context of time, ongoing therapy or no therapy.

Sample Size:

Total Sample size is 56. Anticipated accrual is 2-3 patients a month.

Estimated Duration of the Study

24 months

Summary of Subject Eligibility Criteria:

Patients with 2 PSA values ≥ 0.2 ng/mL at least 4 weeks after surgery will be evaluated. Patients who were started on androgen deprivation therapy will not be allowed on this protocol. Patients who have started radiographic evaluation and underwent CT scan and/ or BS prior to registration to the study will be able to participate under a late registration provision, provided that WB/axial MRI and F-18 NaF PET/CT can be completed within 4 weeks of the CT scan and BS.

Investigational Product Dosage and Administration:

Not Applicable.

Clinical Observations and Tests to be Performed:

CT of the chest, abdomen and pelvis and bone scan. Targeted X Rays if suggested by the radiologist. If negative, WB/axial MRI and F-18 Sodium Fluoride PET /CT. Biopsy of suspected lesions will be performed if feasible, and repeat scans will be performed for patients with suspicious lesions.

Statistical Considerations:

Sponsor/Licensee:

City of Hope

Case Report Forms

Table of Contents

SECTION	PAGE
1.0 Objectives	8
2.0 Background.....	9
2.1 Introduction/Rationale for Development	9
2.2 Overview of Proposed Study	11
3.0 Patient Eligibility	12
3.1 Inclusion Criteria	12

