5.2 Planned Duration of the Study

5.2.1 The initial imaging studies will be performed within 8 weeks of registration on the protocol, Subsequent follow up imaging will be performed within 4-6 months after registration to the study.

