10.2 Follow-up scans

Evolution of lesions over the period of time provides invaluable help in the verification of original interpretation of the scans even in the absence of biopsy. Therefore all the patients will undergo follow up scans (the type advised by radiologist) 4-6 months after registration to the protocol. These scans will be interpreted in the context of ongoing therapy (i.e. hormonal therapy) or observation. Several possible scenarios will allow us to interpret and verify the findings on the original scans.

- a) The persistence, growth, increase in numbers and intensity of enhancement of lesions in patients on observation would strongly favor the interpretation of a true positive finding.
- b) Complete stability over time or resolution of lesions without ongoing therapy would strongly favor false positive interpretation.
- c) Evolution of lesions (regression, radiologic signs of healing in the context of ongoing hormonal therapy (and lack of any history of trauma) would strongly support the interpretation of true positive scans
- d) Complete stability of lesions despite ongoing hormonal therapy would favor false positive interpretation

By combining these three elements of verification of original interpretation of WB/axial MRI and F-18 NaF PET/CT we will be able to provide the most robust assessment of sensitivity and specificity of these imaging modalities in the literature that may prove to be quite useful in the management of patients with biochemically recurrent prostate cancer.

Table 1

Interpretation of Imaging with WB/axial MRI and F-18 NaF PET/CT based on subsequent biopsy, therapy and follow up imaging (not all patients will be classified as below depending on additional systemic therapy given)

Original MRI/PET Interpretation	Biopsy	PSA response to salvage RT	Follow up scans	FINAL Interpretation of Baseline MRI/PET	
Mets	+	NA	Regardless	TP	
			Mets	Indeterminate	
			Indeterminate	FP	
			No mets	FP	
		≥ 0.04	Mets	TP	
	- or NA		Indeterminate	TP	
			No mets	Indeterminate	
	NA	Mets	TP		
		Indeterminate	TP		
		No mets	FP		
Indeterminate	+	NA	Regardless	TP	
			Mets	Indeterminate	
			Indeterminate	FP	
		≥ 0.04	No mets	FP	
			Mets	TP	
	- or NA	≥ 0.04	Indeterminate	TP	
			No mets	Indeterminate	
		NA	Mets	TP	
			Indeterminate	Indeterminate	
			No mets	FP	
Negative	N/A	<0.04	Mets	Indeterminate	
			Indeterminate	TN	
			No mets	TN	
		≥ 0.04	Mets	FN	
			Indeterminate	FN	
			No mets	Indeterminate	
		NA	Mets	Indeterminate	
			Indeterminate	TN	

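### Six statements give conflicting rules for who has the 4-6 month verification scan, and the interpretation table cannot classify a scan-negative patient who is not rescanned

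*Combined protocol and SAP*

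**What the plan says.** The combined protocol and SAP states who has the follow-up scan six times:

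- Synopsis, study design text: "all patients without biopsy proven metastasis will undergo follow up imaging studies".
- Synopsis, clinical observations and tests: "repeat scans will be performed for patients with suspicious lesions".
- Section 5.2.1, with no subgroup named: "Subsequent follow up imaging will be performed within 4-6 months after registration to the study".
- Section 9.0, calendar footnote f: "In patients in whom the results of all the imaging studies and biopsy (if performed) were not conclusive for metastasis".
- Section 10, endpoint evaluation: "perform 4-6 month follow up scans if clinically indicated".
- Section 10.2, Follow-up scans: "Therefore all the patients will undergo follow up scans (the type advised by radiologist) 4-6 months after registration to the protocol".

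Sections 5.2.1 and 10.2 in effect agree, so there are five distinct rules.

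The follow-up scan is one of three elements (with biopsy and PSA response to salvage radiotherapy) that the interpretation table closing Section 10.2 uses to label the baseline MRI/PET read TP, FP, TN, FN or indeterminate. From these elements the protocol promises "the most robust assessment of sensitivity and specificity of these imaging modalities in the literature". The synopsis also names sensitivity and specificity as a purpose of follow-up. Section 12.0 adds that the final judgement of success will take the follow-up scans into account. Neither section says how patients without a follow-up scan are handled.

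**The concern.** A patient negative on both newer scans is rescanned under some of these statements and not under others, so two coordinators could each follow the protocol and verify different patients. Such patients are not directed to biopsy (calendar footnote e; the table shows N/A). The table's only other check on them is PSA after salvage radiotherapy, which Section 10.2 expects to be offered to most patients, not all.

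If the narrower statements are followed, whether a patient's true state is checked can depend on the result of the test being evaluated. That is partial verification, and it distorts the sensitivity and specificity that the protocol sets out to report.

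**Working it through.** **1. What each statement does with a patient negative on MRI and PET**

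| Place | Scan-negative patient |
|---|---|
| Synopsis, design text | Included (no biopsy-proven metastasis) |
| Synopsis, tests | Left out (no suspicious lesion) |
| Section 5.2.1 | Included if read literally |
| Calendar footnote f | Included (not conclusive for metastasis) |
| Section 10 | Left to discretion |
| Section 10.2, Follow-up scans | Included |

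Four statements include him, one leaves him out and one leaves it open. Footnote f also makes the verification of positives unclear: a scan-positive patient without biopsy could be exempt if imaging alone is read as conclusive. Section 10.1.1 expects biopsy in only about 25% of cases with suspicious lesions.

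**2. What the table needs for baseline-negative patients**

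| PSA after salvage RT | Follow-up: mets | Follow-up: indeterminate | Follow-up: no mets |
|---|---|---|---|
| <0.04 | Indeterminate | TN | TN |
| ≥0.04 | FN | FN | Indeterminate |
| NA | Indeterminate | TN | TN |

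All nine cells require a follow-up result, and none covers a scan not done. PSA alone does not settle a row. The table's caveat that some patients will go unclassified refers to systemic therapy, not to missing scans.

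**3. The plan's own figures.** The documents give no value for sensitivity, specificity or the share verified. The figures they do give belong to the primary rule in Section 12.0, at least 4 positives in 45. By exact binomial, P(X ≥ 4) is 0.0456 at a 3% rate and 0.9215 at a 15% rate. The stated bounds (under 5% and over 86%) hold. The rule counts baseline positives, so rescanning scan-negative patients cannot change the count.

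**4. Illustration of partial verification**

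Inputs: 49 patients negative on standard scans (Section 12.0). Assumptions, not in the documents: 50% with metastases (Section 12.0 says only more than half), true sensitivity 20%, true specificity 95%, all positives verified, and a share v of negatives verified irrespective of true state.

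Expected counts:
- TP = 24.5 × 0.20 = 4.9 and FN = 19.6
- FP = 24.5 × 0.05 = 1.225 and TN = 23.275

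With unverified negatives dropped, apparent sensitivity = TP/(TP + v·FN) and apparent specificity = v·TN/(v·TN + FP).

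| v | Sensitivity | Specificity |
|---|---|---|
| 1 | 20% | 95% |
| 0.5 | 4.9/14.7 = 33% | 11.64/12.86 = 90% |
| 0.25 | 4.9/9.8 = 50% | 5.82/7.04 = 83% |
| 0.1 | 4.9/6.86 = 71% | 2.33/3.55 = 66% |

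With an assumed sensitivity of 30% instead, v = 0.5 gives 7.35/(7.35 + 8.575) = 46%. Specificity is again 90%.

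**5. Direction and bounds at v = 0.5.** The unverified negatives number 9.8 + 11.64 = 21.44.
- All counted as TN: sensitivity 33%, specificity (11.64 + 21.44)/(11.64 + 21.44 + 1.225) = 96%.
- All counted as FN: sensitivity 4.9/(4.9 + 9.8 + 21.44) = 14%, specificity 90%.

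The ranges, 14-33% and 90-96%, contain the assumed 20% and 95%.

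**6. Scans ordered on indication.** If missed disease is rescanned more often (assume 80% of FN and 30% of TN), sensitivity is 4.9/(4.9 + 15.68) = 24% and specificity is 6.98/(6.98 + 1.225) = 85%.

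**The case against.** Most of the text already sends scan-negative patients to the follow-up scan. The two outliers are a one-line synopsis summary that does not say only, and a run-on fragment in Section 10 that may come from a flow diagram. Both are nonetheless current protocol text, and one of them sits in the endpoint section.

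Verification does not rest on the scan alone. PSA is scheduled at weeks 16-24, 28-36 and 40-52. The synopsis records PSA and outcome for anyone without a positive biopsy. Item (b) of the PSA-response section calls normal scans with detectable PSA after radiotherapy a false negative, with no scan condition. This stands: these patients are not wholly unverified. But the table does not follow item (b). It returns indeterminate when PSA is ≥0.04 and the follow-up scan shows no metastases, so whether a scan was done can change the label.

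The illustration also simplifies the table, and this stands too. FN requires PSA ≥0.04 after radiotherapy, so rescanning a scan-negative patient who had no radiotherapy can never yield FN, and rescanning everyone would not by itself recover true sensitivity. Not all positives will be verified either, and baseline-indeterminate reads are ignored.

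A reader might infer three stronger things that the documents do not support:
- That scan-negative patients will mostly go without a scan. Four of the six statements include them, a clinical indication need not follow the MRI/PET read, and no rate is given.
- That specificity must fall. The direction depends on how unverified negatives are handled.
- That the primary result is compromised. The count is untouched, and sensitivity and specificity are not among the objectives in Section 1.0 or the endpoints in Section 12.0.

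**Conclusion.** The contradiction is real and should be resolved. If a narrower statement is followed, verification can depend on the baseline read. Apparent sensitivity is then inflated. Apparent specificity falls if unverified negatives are dropped and rises if they are counted as TN.

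The size cannot be fixed from the documents. The step from 20%/95% to 33%/90% with half of negatives verified shows the mechanism under stated assumptions and is not a forecast. The effect is on the sensitivity and specificity assessment and possibly on the final determination of success, for which Section 12.0 gives no formula.

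**What to change.** Reconcile the six statements to one rule. Which rule is for the sponsor to decide; the decision should recognise that the table's TN and FN rows need follow-up results for scan-negative patients.

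In the analysis, under whichever rule is adopted:

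- Classify patients without a follow-up scan as unverified. Biopsy-positive patients are the exception, because the table makes them TP regardless of the follow-up scan.
- Report the number verified by baseline read: positive, indeterminate, negative.
- Give sensitivity and specificity with bounds that treat unverified negatives as all TN and as all FN.

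The cost is a text reconciliation, one extra table and wider reported ranges. The sample size and the 4-of-45 rule do not change. Whether more scans are needed depends on the rule the sponsor adopts.
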